5.2.3 Exclusion Criteria

- 1. Presence of OA of other major joints (including but not limited to nontarget knee) that could interfere with assessment of pain due to OA of the target knee, in the opinion of the investigator.
- 2. Current comorbid condition, other than OA, affecting target knee or systemic illness known to be significantly associated with arthritis or joint pathology affecting any joint, including but not necessarily limited to endocrinopathies or autoimmune disease with significant joint involvement (e.g., Rheumatoid Arthritis); Seronegative Spondyloarthropathies (e.g. Ankylosing Spondylitis, Psoriasis arthritis, Reactive arthritis)
- 3. Pathological conditions significantly affecting joint and bone health, in the opinion of the Investigator should be excluded (including but not necessarily limited to following findings on x-rays and/or MRI):
 - Known presence of Rapidly Progressive Osteoarthritis (RPOA) (any joint)
 - Osteonecrosis (including avascular necrosis) (any joint)
 - Subchondral insufficiency fractures (SIF) (any major joint)
 - Fractures or stress reactions with radiographic signs of ongoing healing processes (including but not limited to osteoporotic and pathological fractures) (any major joint)
 - Excessive malalignment of the knee (anatomical axis angle greater than 10 degrees) (Target knee only)
 - Complete tear of the posterior meniscal root (partial tears and/or anterior meniscal tears not excluded) (either knee)
 - Large or extensive subchondral cysts (either knee)
 - Anserine or patellar bursitis (Target knee only)
 - Significant articular bone loss (any joint)
 - Articular bone fragmentation or collapse (any joint)

Version

Version 3.0_07FEB2023

- Primary or metastatic tumor (any joint)
- Joint infection (any joint)
- Paget's disease (any joint)
- Osteochondritis dissecans (any joint)
- 4. Hip dislocation and congenital hip dysplasia with degenerative joint disease should be excluded.
- 5. History of gout, or pseudogout, unless on hypouricemic therapy (including allopurinol) and no episodes within the last 12 months.
- 6. Presence of neuropathic pain deemed likely to interfere with trial endpoints, complex regional pain syndrome, or chronic widespread pain syndromes e.g., fibromyalgia
- 7. History of significant trauma (e.g., intra-articular fracture) or surgery (excluding injection therapies and arthroscopy) to a knee, hip, or shoulder within the previous 1 year or previous target knee alloplasty
- 8. Planned major surgery or other major invasive procedures while participating in the study
- 9. Surgery or stent placement for coronary artery disease in the six months prior to screening
- 10. Nondiagnostic arthroscopy performed on the target knee joint within 180 days prior to Screening; or diagnostic arthroscopy performed on the target knee joint within 90 days prior to Screening
- 11. Intraarticular injection therapies to the target knee joint within 12 weeks prior to Screening, or to any non-target major joint within 6 weeks prior to Screening
- 12. Participants likely to be deemed unfit for joint replacement surgery due to concomitant illness, in the investigator opinion
- 13. Opioid use, including Tramadol, of 4 or more instances per week over the month prior to Screening
- 14. Known history of hypersensitivity to monoclonal antibodies
- 15. Presence of any medical condition or unstable health status that, in the judgment of the investigator, might adversely impact the safety of the participant or efficacy results of the trial
- 16. Medical history and/or clinical findings (including ECG) of cardiac disease that in the opinion of the investigator are considered of clinical significance, including but not limited to established ischemic heart disease, peripheral arterial disease and /or cerebrovascular disease (unstable angina, myocardial infarction, cardiovascular thrombotic events, transient

Version

Version 3.0_07FEB2023

ischemic attacks, and stroke are considered clinically significant if time of event occured within six months prior to screening)

- 17. Active malignancy or history of malignancy within the past 5 years, with exception of resected and cured basal cell carcinoma and squamous cell carcinoma of the skin
- 18. Clinically significant abnormal laboratory parameter(s) and/or electrocardiogram (ECG) parameter(s) during Screening, that, in the judgment of the Investigator, would preclude the participant from participation in this study
- 19. Participation in other studies involving investigational drug(s) within 30 days (or 90 days for biologics) prior to screening
- 20. History of Carpal Tunnel Syndrome with signs or symptoms within one year of Screening or a Boston Carpal Tunnel questionnaire (Symptom Severity Scale mean score ≥3)
- 21. Total score on Number of Symptoms (Column Q1a) on the SAS >3
- 22. Pregnant or breast feeding
- 23. Previously received any form of anti-Nerve Growth Factor (NGF)
- 24. Requires walker or wheelchair for mobility (walking stick permitted)
- 25. Active or historic substance abuse within one year of Screening in the opinion of the Investigator
- 26. Medical history within 5 years of Screening that involves suicidal ideation, suicide attempt, or increased risk of suicide as assessed by the Investigator.
- 27. Presence of any contraindication to MRI, including partial or total joint replacements that are expected to interfere with the quality of the imaging

5.3 Criteria for Initiation of Trial Treatment

Pain Assessments

As an essential part of the eligibility determination process, participants will be evaluated based on following pain instruments: The WOMAC Pain subscale, and Average Daily NRS Pain.

The WOMAC Pain subscale NRS 3.1 (WOPAIN NRS) will be completed for both knees during Screening prior to starting the Diary Run-In Period, with the requirement that the participant is treatment naïve or has not used analgesics during the 48 hours prior to completion and must be ≥20 out of 50. Participants at Visit 1 who have taken analgesics the 48 hours prior to Visit 1 will have WOPAIN NRS completed prior to or at Visit 2 following the 48-hour analgesic washout.

Version Version 3.0 07FEB2023

The Baseline NRS Pain score will be derived from the Average Daily NRS Pain score collected on the last seven days of the Diary Run-In Period (Day 10 - Day 14) and at least one knee must meet the criteria as described in inclusion criterion 9.

• Radiographic Assessments

For evaluation of relevant Inclusion and Exclusion criteria radiographs of both knees and both shoulders and hips will be taken during the Screening period and at the end of the study. Knee radiographs acquired within three months prior to Screening may be submitted for central reading, provided they meet the study requirements for acquisition and quality. Participants with partial or total joint replacements of any minor and major joints are not excluded from the trial, if the participant is otherwise considered eligible and central radiographic responsible personnel consider the prothesis compatible and safe upon imaging with results at sufficient quality. Conversely, any partial or total knee replacement of the target knee is exclusionary.

Participants with non-target knee joint replacements may however, pending the central radiographic assessment be considered ineligible as the radiographic assessments may provide additional information on joint and bone health related to the joint replacement, which could render the participant unsuitable for the study.

MRI Assessments

Participants will have MRI of both knees conducted prior to Randomization and read centrally for confirmation of eligibility and selection of Target Knee. A follow-up MRI of the Target Knee only will be performed at FU/EOT.

5.4 Withdrawal from Trial Therapy/Early Termination

All participants will be informed that they are free to withdraw from study participation at any time, for any reason, and without prejudice. If a participant withdraws consent to participate or enrolls in another clinical trial (any sub-trial or extension trial in relation to LEVI-04 excluded), it should be adequately reviewed if an adverse event is given as the primary reason for withdrawal.

The Investigator may withdraw a participant from the study for the following reasons:

- Pregnancy
- Significant study non-compliance or protocol deviations
- If any clinical AE, laboratory abnormality, or other medical condition or situation occurs such that continued participation in the study would not be in the best interest of the participant.
- If the participant meets an exclusion criterion (either newly developed or not previously recognized) that precludes further study participation
- The study is no longer in the best interest of the participant.

Version Version 3.0 07FEB2023

5.4.1 Process for Early Termination

In case a participant discontinues trial prior to completion, the Investigator must make every effort to schedule and complete an EOT visit 4 weeks +/- 3 days following last administration of IMP and a Follow-up Safety Phone Visit (minimum 12 weeks following last dose of IMP). The assessments and procedures to be completed at EOT visit for participants that have withdrawn from study prior to completion and received at least one dose IMP, are as listed for FU/EOT Visit 11 and Safety Follow-up Phone Visit 12. It should be assessed if a TEAE was the primary reason for withdrawal. In this case, the TEAE must be documented, reported, and followed as described in Section 9.1.1.

Reason for participant withdrawal from the study and the date of discontinuation will be recorded on the electronic Case Report Form (eCRF).

A participant will be considered lost to follow-up if he or she fails to return for any scheduled visit and is unable to be contacted by study site staff. Should the participant continue to be unreachable 6 months after IMP administration, he or she will be considered to have withdrawn from the study with a primary reason of lost to follow-up.

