Urine Dipstick hCG					X		X		X	X	X		X	

CONFIDENTIAL

Clinical Trial Protocol

LEVI-04-21-02

Version

^{*}All participants should complete Visit 11 and Visit 12. If a participant has discontinued trial early (prior to completion of Visit 10), the EOT/FU visit should be completed at 4 weeks (+/-3 days) of last IMP dose received and the Follow-up safety visit (phone visit) be scheduled at least 12 weeks following last IMP administration.

¹Participants are required to stop any analgesic medication at the start of the Diary Run-In Period and until completion of visit 11 FU/EOT visit. Rescue Medication will be provided (Paracetamol, max 4000 mg/day), but participants must be discouraged from taking it, particularly in the 48 hours prior to visits.

²Review of contraception use for WOCBP and male participants with female partners of childbearing potential.

³Review usage of illicit and recreational substances

⁴Ensure participant is eligible on all inclusion/exclusion criteria

⁵Selection of Target Knee after completion of the Diary Run-In Period and MRI of both knees has been read.

⁶Radiographs of both knee-, shoulder- and hip joints can be performed at any time prior to Visit 2 as long as they have been evaluated for eligibility prior to Visit 2

⁷MRI to be completed for both knees during Screening and reviewed for eligibility prior to selection of Target Knee at Visit 3. MRI of Target Knee only at study completion (FU/EOT visit)

⁸Ensure that the participant understands how to use the eDiary daily for completion of Average Daily NRS Pain score(s) and recording of any use of Rescue Medication. Accurate Pain Reporting (APR), Placebo Response Reduction (PRR) and Research Subject Responsibility (RSR) training to be completed at Visit 2 and Visit 3. Training modules to be repeated if indicated.

⁹WOMAC Pain subscale (WOPAIN NRS) for both knees to be completed during Screening prior to starting the Diary Run-In Period. The participant is required to abstain from taking analgesics in the 48-hours prior to completion or be treatment naïve. If not completed at Visit 1, WOPAIN NRS can be completed at Visit 2.

¹⁰Rescue Medication (Paracetamol) dispensation, and use of Rescue Medication accounted for.

¹¹BMI calculated automatically in EDC

¹²Serum hCG to be collected during Screening for WOCBP. If needed, safety labs can at all later timepoints include a Serum hCG.

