8.5 Follow-up Period

8.5.1 Visit 11 (Week 20, Day 141 ±3 days): Follow-up Visit/End of Trial Visit

The assessments and procedures as described below apply to Visit 11 and EOT visit for participants that have discontinued trial prior to completion of Visit 10 procedures and assessments. For participants that have discontinued trial early, the EOT visit should be attempted completed within 4 weeks (+/- 3 days) following last received IMP administration.

- Review of 48-hour washout of Rescue Medication prior to visit.
- Assessment of changes in concomitant medication.
- Review of new potential AEs and follow-up on ongoing AEs
- Survey of Autonomic symptoms
- BCTQ
- Vital signs
- Weight measurement
- BMI calculated automatically in EDC
- Physical exam (including Musculoskeletal Examination)
- Blood sample for:
 - o Safety Hematology and Chemistry
 - o PK blood sample to be collected
 - ADA to be collected
 - o PD biomarker sample to be collected
- Urine dipstick hCG for Women of Childbearing Potential
- Final accountability of Rescue Medication
- Radiographs bilateral knee-, shoulder- and hip joints
- MRI Target Knee

Version Version 3.0_07FEB2023

8.5.2 Visit 12 (Week 30, Day 212 ±7 days): Follow-up (FU) Safety Phone Visit

Site will contact the study participant per phone to complete following assessments:

- Assessment of changes in concomitant medication
- Review potential new AEs and follow-up on ongoing AEs. See Section 9.4 for description on procedure for AEs ongoing at Visit 12.

9 Assessment of Safety

The safety profile of the IMP will be assessed through the recording, reporting, and analysis of baseline medical conditions, AEs, physical examination findings including vital signs and laboratory tests and procedures, including ECGs in Screening and prior to each dosing. Safety assessments to be performed as per the:

- Interim Analyses Charter
- Independent Adjudication Committee for Adverse Events relating to Joint Safety Charter
- Medical Monitoring Plan
- Pharmacovigilance Plan
- Safety Monitoring Committee Charter

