10.4.5 Analysis of Primary Endpoints

The primary population of all efficacy analyses will be the Intent-to-Treat populations defined as all randomized participants. The primary efficacy analyses of continuous data will be analyzed using the ANCOVA model of the change from baseline in score, with treatment, study center, and baseline score as covariates. The primary timepoint for analysis will be week 17. Because of the IA, the final analysis will be conducted between each of the three treatment arms and placebo using a simple combination test (1/2 weight on interim Z, and 1/2 weight on final Z) at a two-sided 0.0188 level of significance (due to Dunnett's adjustment).

The WOMAC pain sub-score will be tabulated per time point (visit) and treatment group, along with the absolute change from baseline where baseline is defined as the latest assessment prior to first treatment administration.

For the treatment effect testing of IMP versus placebo, the null and the alternative hypothesis will be:

H0: Mean (Placebo) = Mean (IMP)

H1: Mean (Placebo) \neq Mean (IMP)

If the null hypothesis is rejected, the alternative hypothesis will be accepted, and it will be concluded that the treatment effect of IMP differs from placebo.

To assess the robustness of the primary results, sensitivity analysis will be performed with modification of participant population (MITT and PP Analysis Sets). Further investigation of the robustness of the primary results (in particular, the influence of time and covariates) may be performed, if deemed necessary.

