4.9 Missing data

The WOMAC osteoarthritis index is a self-administered questionnaire consisting of 24 items divided into three subscales: pain (5 items), stiffness (2 items), and physical function (17 items). Scores for the subscales are based on the sum of the responses (each ranging from 0, no symptoms, to 10, worst imaginable) within the subscale. If participants fail to complete all questions, then missing responses will be imputed as the mean of the non-missing responses within the same subscale provided that:

LEVI-04-21-02 Statistical Analysis Plan	Version: Final 3.0
Date: 18-Mar-2024	Page 18 of 34

- Pain Subscale: no more than one response is missing,
- Stiffness Subscale: no more than one response is missing,
- Function Subscale: no more than three responses are missing.

If the number of missing responses for a given subscale meets the specified criterion, then the overall score for the subscale is calculated according to the non-missing and imputed responses and considered as an observed response. If more than the specified number of responses is missing, the subscale is considered invalid and the subscale score is considered missing. All non-missing responses will be presented in listings regardless of the number of missing responses.

Missing data for the primary endpoint (WOMAC pain subscale score) will be imputed using multiple imputations (MI) methodology. All missing visits data will be imputed using all prior visits data as well as treatment. Data that is missing at random will be imputed using the randomized treatment assignment, whereas data that is missing due to treatment (adverse event, lack of efficacy) will be imputed using placebo as the treatment. For the MI model, 100 imputations will be generated using PROC MI of SAS®. Fully conditional specification (FCS) model using the regression method will be used with non-missing baseline and post-baseline WOMAC pain subscale, and other important covariates to impute any missing data including missed visits and missing data due to dropouts. The seed to be used is 20220420. The results from the MI will then be used to derive the value of the change from baseline in the WOMAC pain subscale score at each timepoint, and then analyzed using the analysis of covariance (ANCOVA) model. The results of the 100 analyses will be transformed into a normal statistic and combined into a single analysis using PROC MIANALYZE.

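### Participants who leave the trial before Visit 10 get an End-of-Trial visit without WOMAC and are not asked for a Week 17 score, so their primary value rests on imputation alone

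*Protocol*

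**What the plan says.** After randomization, the Schedule of Events (Protocol Table 1) places WOMAC at Visit 6 (Week 5) and Visit 10 (Week 17) only. Dosing Visits 7, 8 and 9 do not include it.

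For early leavers, the footnote to Table 1 reads "If a participant has discontinued trial early (prior to completion of Visit 10), the EOT/FU visit should be completed at 4 weeks" of the last dose. Protocol 5.4.1 says that "the Investigator must make every effort to schedule and complete an EOT visit 4 weeks +/- 3 days following last administration of IMP", and that the procedures at that visit "are as listed for FU/EOT Visit 11 and Safety Follow-up Phone Visit 12". Protocol 8.5.1 confirms that its list is to "apply to Visit 11 and EOT visit for participants that have discontinued trial prior to completion of Visit 10 procedures and assessments".

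The Visit 11 list has the autonomic symptom survey, the carpal tunnel questionnaire, vital signs, examination, bloods, radiographs of knees, hips and shoulders, target-knee MRI and a review of the rescue washout. WOMAC, PGA and StEPP are absent from it in the synopsis, in Table 1 and in 8.5.1.

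On analysis, Protocol 10.4.5 states: "The primary population of all efficacy analyses will be the Intent-to-Treat populations defined as all randomized participants". The primary timepoint is Week 17. SAP 4.9 multiply imputes missing WOMAC pain scores. Scores missing at random are imputed under the randomized arm, "whereas data that is missing due to treatment (adverse event, lack of efficacy) will be imputed using placebo as the treatment".

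**The concern.** The primary question covers everyone randomized, yet a participant who leaves before Visit 10 has no planned WOMAC after leaving. Someone who leaves between Weeks 5 and 17 has a last score up to 12 weeks before the endpoint, and it may predate whatever made them leave. Someone who leaves before Week 5 has only baseline.

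The Week 17 value then comes wholly from a model. For adverse-event and lack-of-efficacy leavers, that model assumes an outcome like placebo. The assumption may be sensible, but the plan collects nothing to check it against, even though it tries to bring these participants in for imaging and blood tests. The sensitivity analyses named in SAP 4.11 change the population to mITT or PP and use observed data only. They drop the imputed values and do not try another assumption. Further robustness work is optional.

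**Working it through.** **1. The plan's own power, to see whether the loss is already allowed for.** Inputs from Protocol 10.1 and SAP 4.3: N = 416 in four equal arms (104 each), difference 10, SD 19.2, 15% dropout, two-sided 0.0188 per comparison, equal-weight combination of interim and post-interim Z. The two-sided Dunnett critical value for three comparisons solves to 2.349, as SAP 7 states.

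- Retained per arm: 104 × 0.85 = 88.4.
- One comparison: expected Z = 10 / (19.2 × √(2/88.4)) = 3.46. Power = P(Z > 2.349 − 3.46) = 86.7%.
- At least one of three comparisons, by simulation: 90.6%, 87.6% and 87.8% for the three scenarios, against 90%, 88% and 86% stated. All nine entries for N = 624 agree within 2 points.

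The stated power reproduces with 15% removed, so there is no sample-size error here.

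**2. How many Week 17 scores are missing through dropout.** The plan spreads 15% evenly over the study without saying whether that means 17, 20 or 30 weeks. For a spread over T weeks, the number leaving by Week 17 is N × 0.15 × 17/T, and by Week 5 it is N × 0.15 × 5/T.

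| Spread | N = 416: no Week 17 score | Of these, baseline only | Of these, Week 5 last | N = 624: no Week 17 score |
|---|---|---|---|---|
| 17 weeks | 62.4 | 18.4 | 44.0 | 93.6 |
| 20 weeks | 53.0 | 15.6 | 37.4 | 79.6 |
| 30 weeks | 35.4 | 10.4 | 25.0 | 53.0 |

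The documents give the study duration as 30 weeks, so 35 is the literal reading and 62 is the upper end.

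**3. Whether the EOT visit could stand in for Week 17.** Dose day plus 28 gives nominal EOT days 29, 57, 85, 113 and 141. The Visit 10 window is Day 117 to 123, and none of these falls in it. The nearest is the leaver last dosed at Week 12 (Day 85 + 28 = Day 113). Only a late dose plus a late EOT (85 + 3 + 28 + 3 = Day 119) could reach the window, and WOMAC is still not listed. Adding WOMAC at EOT would therefore inform the imputation but not remove it.

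**4. What the unknown outcomes could do.** Suppose 15% of an active arm leaves before Week 17 and leavers lose a fraction f of a 10-point effect. The difference over all randomized is then 10 × (1 − 0.15f). The documents give no value for f. With all 104 per arm observed, in the scenario with one effective arm:

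- f = 0: difference 10, power 92.9%.
- f = 0.5: difference 9.25, power 88.1%.
- f = 1: difference 8.5, power 81.4%.

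If only 8.5% leave by Week 17 (15% × 17/30), f = 1 gives 9.15 and 87.3%. These figures show how far the target quantity can move. They do not estimate bias.

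**The case against.** Several points on the other side stand.

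- **Leaving the trial is not the same as stopping infusions.** A reader might infer that everyone who stops treatment loses Week 17. The documents do not support this. The early-termination text governs those who discontinue the trial. Protocol 12.2 records withdrawal from trial or from study drug separately, the PP set in SAP 4.5 allows for a missed administration, and SAP 4.15 has a subgroup for missed infusions. Such participants can attend Visit 10. What remains is that Protocol 5.4 sets out no explicit path for stopping infusions while staying under assessment.
- **Attendance is not assured.** A reader might infer that all leavers are seen in clinic and their scores simply not taken. The visit is a best-effort one, for those with at least one dose, and participants may refuse or be lost. The counts above are all dropouts, not recoverable ones.
- **Pain data are not absent.** Target-knee daily NRS pain is scheduled up to Visit 11/EOT. SAP 4.9 also admits further covariates to the imputation model, although it does not name the diary.
- **An observed Week 17 score would already be used.** Only missing scores are imputed, and SAP 4.9 re-imputes at study end from all available data.
- **Late scores are not clean.** Protocol 6.4.3 lifts the analgesic restrictions after EOT. With EOT at Day 29, 57 or 85, a Day 120 score would come 91, 63 or 35 days after they ended. Membership of the ITT set does not settle how such a score should be read; that needs an intercurrent-event strategy. The list of intercurrent events in SAP 3 is cut off in the available text, so I draw nothing from it.

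These points narrow the gap but do not close it. The observed-data analyses do not examine the placebo-based rule, and the diary is a different instrument from the primary one.

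**Conclusion.** The point holds for participants who discontinue the trial before Visit 10. Their planned path yields no WOMAC after leaving, and their Week 17 value in the ITT analysis is imputed under an assumption that no named analysis tests. On the plan's 15% dropout this is about 35 to 62 of 416, or 53 to 94 of 624, depending on how dropout is spread. At N = 416, about 10 to 18 of them would have baseline only.

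Three quantities are not in the documents: the share who leave for adverse events or lack of efficacy, the share who would attend EOT or give a later score, and the share of effect that leavers keep. No direction or size of bias can therefore be stated. It would also be wrong to read this as a power shortfall or a promised power gain. The 15% loss is already in the sample size, and with leavers observed power could be higher or lower than stated.

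One related wording needs reconciling. Protocol 10.4.3 ends by ruling out imputation when a whole questionnaire is missing, which conflicts with its own text on the primary endpoint. The SAP does not repeat that sentence, and I have followed the SAP.

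This is a worthwhile, cheap improvement to a design choice, not an error.

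**What to change.** 1. **Protocol Table 1 and 8.5.1:** add the five-item target-knee WOMAC pain subscale to the EOT visit for those who discontinue before Visit 10.
2. **Protocol 5.4.1:** state that participants who leave early but have not withdrawn consent to contact are asked for a WOMAC pain score at Week 17 (Day 120 ±3), remotely if needed, with analgesic use recorded.
3. **SAP 4.9:** include the EOT WOMAC, with its timing, as a predictor in the imputation model. State how Week 17 scores obtained after discontinuation are used under the estimand, at least in a sensitivity analysis of the placebo-based imputation.

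The cost is a short amendment, five items at a visit already planned, and one remote contact for willing leavers. The participant burden is slight. EOT scores will not be at Week 17, and some Week 17 scores will be off drug and after analgesic restrictions have ended, so the analysis rule in item 3 should be fixed before unblinding. No dosing or clinical rule changes.
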